**Table 2 Two by two table: definitions of test and disease status.**

	Index positive	Index negative
Reference standard positive: nAMD	True positives Any reference standard indicates nAMD in study eye AND Any index test result is positive during valid follow-up period	False negatives Any reference standard indicates nAMD in study eye AND Index test negative for all available prior time points
Reference standard negative: No nAMD	False positives All reference standard results indicate no nAMD in study eye AND Any positive index test result during valid follow-up period	True negatives All reference standard results indicate no nAMD in study eye AND Index test negative for all available prior time points

Sensitivity and specificity will be calculated with 95% confidence intervals calculated using the Agresti-Coull method (Zhou 2002). Positive and negative likelihood ratios will also be calculated with 95% confidence intervals calculated using the method in Zhou 2002. Diagnostic odds ratios and the proportion of indeterminate tests will be calculated with 95% confidence intervals. A ROC curve will be plotted and the area under the ROC curve calculated using the trapezoidal rule for visual acuity tests. The standard error for the AUC will be calculated using the method of DeLong, DeLong and Clarke-Pearson (1998) and used to form an asymptotic normal 95% confidence interval.

Monitoring sensitivity and specificity of the tests will be compared using McNemar's statistical test (with 95% confidence intervals produced using Newcombe's method) (Newcombe 1998).

For comparing sensitivities under the primary analysis, the McNemar 2x2 table will be constructed using only patients who have had a positive FFA result. They will be classified as having a positive index test, if the index test has any positive results during the valid follow-up period. They will be classified as having a negative index test, if all prior available tests have been negative during their valid follow-up period. For comparing specificities under the primary analysis, the McNemar 2x2 table will be constructed using only patients who have had negative FFA results throughout using the same index test classification.

Analysis A2 analysing the index tests collapses the index tests as in table 2 but only uses index tests from the individual's last 6 study months (not the entire study period). A positive index test result out-with the 6 months window therefore does not lead to a positive test result at the collapsed individual

level. The individual diagnostic performance of the tests are calculated using this index test definition and the McNemar comparisons of sensitivity and specificity as detailed above.

The third approach to the index tests uses the index test at the individual's last study visit only (Analysis A3). If a participant developed nAMD according to the reference standard during the follow-up period, only the index test data from their visit where nAMD was diagnosed will be used. If they did not develop nAMD during the follow-up period, index test data from the last visit for which their reference standard is available will be used.

Analyses A1, A2 and A3 use the local FFA as assessed by the responsible ophthalmologist as the reference standard. If a participant has a negative local FFA result but exits the study at that point because of a clinical diagnosis of nAMD by the ophthalmologist, then they will be classified as reference standard no nAMD.

Alternative person level diagnostic accuracy analyses are planned that will use two alternative reference standards:

- An alternative reference standard using the FFA result as determined by the reading centre (analysis A4 using all valid index test results, analysis A5 using index tests from the last 6 months and analysis A6 using the index test results from the last visit). Analyses A4, A5 and A6 comprise the individual diagnostic performances of the tests and the McNemar comparisons.
- An alternative clinical reference standard will also be used. A positive clinical reference standard result will be assigned if there is either a positive local FFA or a positive clinical diagnosis. A negative clinical reference standard result will be assigned if there is a negative FFA or an inconclusive local FFA and negative clinical diagnosis or FFA not done and a negative clinical diagnosis. Analysis A7 will use the clinical reference standard as defined above and all the valid index test results will be used. The individual diagnostic performances of the index tests and McNemar comparisons will be included.

A summary of the reference standard and index test definitions and the corresponding analyses is included below

Reference standard definitions:

A = Local FFA. Reference standard is positive if the local FFA indicates nAMD. Reference standard is negative if local FFA indicates no nAMD throughout.

B = Reading centre FFA. Reference standard is positive if the reading centre FFA indicates nAMD at any time point and negative if it indicates no nAMD throughout.

C = Clinical reference standard. Reference standard is positive if the local FFA indicates nAMD or a clinician diagnosis of nAMD at any time point. Reference standard is negative if the local FFA is negative/inconclusive/not done and the clinician diagnosis is negative.

Index test definitions:

A = Collapsed index test results from whole valid follow-up period. Positive if there is any positive index test and negative if the index test is negative throughout. All index tests during the valid follow-up period are used.

B = Collapsed definition from last 6 months of monitoring. Only uses index tests within 6 months of participant's study end date. Positive if there is any positive index test within the final 6 months and negative if the index test is negative throughout the final 6 months.

C = Index test result at participant's last available visit only (within a 3 month window of the last FFA).

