#### Evidence for monitoring intervals/diagnostic performance

When active nAMD is confirmed, treatment with anti VEGF therapy is initiated ([name] 2010, IVAN investigators 2012; Martin 2012). In the early phases of treatment (ie up to about one year), at each subsequent visit which is usually on an 8 week cycle, patients are re-assessed to evaluate disease activity. Visual acuity, clinical biomicroscopic examination and optical coherence tomography (OCT) are the most commonly employed tests in the follow up setting. OCT-guided re-treatment decisions is the standard of care in almost all NHS units, however the combination of VA, clinical examination and fluorescein angiography in selected cases is also used in the monitoring phase ([name] BMJ, Martin 2012). In the absence of disease activity on the tomogram, treatment is withheld and review arranged. Interrogation of the national ophthalmology dataset (NOD), which is an amalgamation of the electronic records of some 14,500 patients who have received anti VEGF treatments since 2009, ([name] is a contributing member) shows that the average number of visits is 10 in year 1 and around 8 in year 2. The average interval in year 1 between visits is 35 days (+/- 10). The interval between visits increases in years 2 to 5. However, even in year 5, more than half of all persons are on regular review and treatment. Thus there is an opportunity to obtain information on unaffected fellow eyes of patients with nAMD in one eye to determine the optimum method of early detection of incipient nAMD.

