#### 3.2. Interventions to be evaluated (Index tests)

As part of routine care for the fellow eye (with nAMD) it is expected that patients will attend regular monitoring visits. The frequency of visits is likely to be between 4 and 8 weekly in year 1 and extended to between 8 and 12 weekly in year two but is contingent on local AMD treatment pathways. The candidate tests which are part of routine clinical practice are performed on both eyes at every visit and therefore the data acquired at these visits on the EDNA study eye will be collected and evaluated:

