#### Follow-up measurements

Data collected at each routine clinic visit during follow-up will be extracted from the medical records. This will include, index test results, indication for FFA, FFA results if requested.

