## **Statistical Principles**

### **Sample size**

The sample size is based upon comparative diagnostic accuracy to ensure the ability to detect differences in sensitivity and specificity between candidate tests. The calculation is based upon McNemar's test. (Obuchowski 1998) Under the primary analysis, a positive candidate test result will be defined as any positive result during the monitoring period on the respective test. At 2-sided 5% significance level and 90% power, a paired difference of 15% (80% to 65%) in sensitivity will require 491 participants (560 allowing for indeterminate/missing data results - including patients lost to follow-up cumulatively of up to 12%) given a cumulative incidence of 28% at 3 years. (Karnon 2008) This calculation assumes a disagreement between tests of 0.30 which was based upon data from a diagnostic study involving OCT for diagnosis glaucoma (HTA reference 09/22/111). A smaller difference in specificity will be identifiable (7%; 94% to 87% with power and significance levels as before) given most participants will not convert during the 3-year follow-up period even if the maximum level of disagreement occurs. The reference sensitivity and specificity values used in this calculation are the values observed for OCT in a pilot study with a similar study design. (Parnick-Silver 2012) Differences in sensitivity and specificity of at least 20% will also be detected at the same power and significance levels even if the sensitivities/specificity are substantially lower (e.g. 60 to 40%) or the level of missing data is higher (e.g. 20%). These calculations conservatively assume maximum possible disagreement between tests. A sample of this size would be of sufficient size for other measures of diagnostic performance (e.g. the sensitivity and specificity of individual technologies will be estimated to 95% confidence interval of width 16% and 10% respectively given a sensitivity/specificity of 65% or higher). Such a sample will also provide a sufficient sample for the GEE analysis given the anticipated gain in precision due to use of multiple repeated measures over

time. (Rochon 1998) Similarly, this sample will be more than sufficient for the development of a risk prediction model with over 130 events (conversions to AMD) anticipated and given 10 events per predictor variable/contract are typically recommended. (Peducci 1995).

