### **Index test result definition for analysis A**

For each index test, multiple test results will be collapsed into a single test result. Any positive test result over the valid follow-up period will be classed as an overall positive result. To be a negative index test result, all index test results must be negative. The classic 2x2 table for assessing diagnostic accuracy with our definitions is provided in Table 2 below.

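### A1 compares index tests over each test's own recorded visits; if recording is less complete for one test, its specificity is flattered and its sensitivity may fall, and no planned analysis compares the tests over common visits

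*SAP*

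**What the plan says.** The collapse rule is in the SAP under Index test result definition for analysis A: "Any positive test result over the valid follow-up period will be classed as an overall positive result". Below Table 2, the McNemar table for sensitivities uses participants with a positive FFA, and "They will be classified as having a negative index test, if all prior available tests have been negative during their valid follow-up period". The table for specificities applies the same classification to participants whose FFAs were all negative.

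Inclusion is decided for each of the five tests separately. A participant whose last FFA is negative needs one earlier result of that test. A participant whose last FFA is positive needs a result in the preceding 3 months; otherwise an earlier FFA is tried. The valid follow-up period ends at whichever FFA qualifies, so it too can differ between tests in the same person.

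On delivery, Protocol 3.2 states that "The candidate tests which are part of routine clinical practice are performed on both eyes at every visit". Protocol 3.6.6 and the SAP section on time points of outcome collection also plan all five tests at each visit. On the source of the data, Protocol section 6 says: "Data collected at each routine clinic visit during follow-up will be extracted from the medical records".

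**The concern.** An any-positive rule depends on how many times a test is recorded. Each extra result is another chance of a false positive in a non-converter and another chance of a hit in a converter. Two tests with the same accuracy at each visit will therefore give different collapsed results if one is recorded less often, and McNemar's test will read the difference as one of accuracy.

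The plan does not guard against this. The missing-data section deals with FFA results and baseline covariates, not with missed index tests. Sensitivity analyses 1 to 6 change the OCT reader, the cut-offs or the handling of indeterminate results; none matches visits.

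Unequal completeness is a real possibility. The protocol's background on routine care says "Visual acuity, clinical biomicroscopic examination and optical coherence tomography (OCT) are the most commonly employed tests in the follow up setting", a list without Amsler or patient report. The SAP's dummy tables count each test done by study year and give each test a row for missing results. At stake is whether a preference for one monitoring test reflects its accuracy or how regularly clinics recorded it.

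**Working it through.** **Inputs from the documents**

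- Design: "At 2-sided 5% significance level and 90% power, a paired difference of 15% (80% to 65%) in sensitivity will require 491 participants"; "This calculation assumes a disagreement between tests of 0.30"; "given a cumulative incidence of 28% at 3 years".
- Specificity pair in the SAP sample size section: 94% and 87%.
- Visits about every 8 weeks for 3 years: 156/8 = 19.5, taken as 19.

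**The plan's own figure.** With d = 0.15 and ψ = 0.30, n = [1.960√0.30 + 1.282√(0.30 − 0.0225)]²/0.15² = 135.9, so 136 converters. 136/0.28 gives 486, within about 1% of the stated 491. Of 491, about 137 convert (491 × 0.28) and 354 do not (491 × 0.72).

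**Assumptions, not in the documents**

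- The second test is recorded at a random share f of visits; f = 0.90, 0.75 and 0.50 are shown.
- Both tests have the same visit-level accuracy.
- Results are independent between visits and between tests, except where stated.

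**Specificity.** If a test done at all K visits has collapsed specificity S, its visit-level specificity is q = S^(1/K). A test done at share f then has collapsed specificity (1 − f(1 − q))^K. For S = 0.94 and K = 19, 1 − q = 0.00325.

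| f | Collapsed specificity | Spurious gap | False McNemar rejection, 354 non-converters |
|---|---|---|---|
| 1.00 | 94.0% | 0 | about 5% |
| 0.90 | 94.6% | 0.6 points | about 6% |
| 0.75 | 95.5% | 1.5 points | about 13% |
| 0.50 | 97.0% | 3.0 points | about 47% |

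The rejection rates are simulated. With 15 or 26 visits in place of 19, the collapsed specificities are the same to one decimal place.

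- From S = 0.87 (1 − q = 0.0073), 75% and 50% delivery give 90.1% and 93.3%. The gaps are 3.1 and 6.3 points, and rejection is about 24% and 81%.
- From 94% with within-person correlation of 0.1 to 0.3, rejection falls to 6–8% at 75% delivery and 15–27% at 50%.
- If a false positive, once present, persists at every later visit, 94.0% becomes only 94.3% at 50% delivery.

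**Sensitivity.** Take a test done at every visit with collapsed sensitivity 80%, which implies 0.794 at the conversion visit. Treat the 3-month window as the conversion visit plus the one before, and drop participants with no result in it.

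- The share of included converters who have the test at the conversion visit is f/[1 − (1 − f)²] = 1/(2 − f): 0.909, 0.800 and 0.667 for f = 0.90, 0.75 and 0.50.
- Multiplying by 0.794 gives 0.722, 0.635 and 0.529. False positives at earlier visits add 1 to 2 points, so the simulated values are about 73%, 65% and 55%.
- False rejection with 137 converters is about 25%, 76% and 97%.
- If the test is always done at the conversion visit, the loss at 50% delivery is at most about 2 points, over visit-level specificities from 98% to 99.67%.

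**Common visits.** Collapsing both tests only over visits at which both were done returns rejection to about 4–6% for both measures. At 75% delivery, starting from 94%, both tests then show specificity 95.5% and sensitivity 65.1%.

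**The case against.** The strongest reply is that the premise is not in the documents. All five tests are scheduled at every visit, self-reported function and Amsler are named among the results to be extracted, and the question on vision is put with standard instructions at each follow-up visit. The list of commonest tests is background on routine care, not the study schedule. An empty completeness table does not show that completeness is poor. The one stated difference, that Amsler is not collected after an abnormal baseline Amsler, removes whole participants from the Amsler analysis and does not give them fewer looks. All of this stands. A reader might infer that Amsler and subjective vision are in fact done less often, and hence that A1 is biased as planned. The documents do not support that: they give no completion rates, and at equal delivery the artefact is zero.

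A reader might also infer that every planned analysis shares the problem. That is not so. A3 and A6 take one result per test per person, so the number of looks cannot matter, and the GEE model (Analysis B) uses results visit by visit. But A3 and A6 describe the last visit and not monitoring over follow-up, A2 and A5 still collapse over 6 months, and the GEE is secondary.

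Third, the size can be overstated. The SAP says its reference values are those observed for OCT; by parallel with 80% to 65%, the natural OCT value is 94%, not 87%. Recurring false positives reduce the specificity effect, and the 3-month rule limits the sensitivity effect. This stands too, and 94% is used as the main case here.

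**Conclusion.** The point holds conditionally. A1 lets the two tests in a McNemar pair rest on different visits, and even on different follow-up periods. If completeness differs, the direction of the specificity error is certain unless false positives persist, when it is close to nil. Sensitivity is materially affected only where the less complete test is missed at the conversion visit.

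The size rests on delivery shares that the documents do not give. At 90% delivery the specificity effect is negligible. At 50% with independent visits it is about 3 points from a 94% start, against the 7 points that the SAP treats as detectable.

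This does not show that A1 is wrong as planned or that it must be replaced. It shows that a difference found in A1 could not be told apart from a difference in recording over the monitoring period, and that a cheap addition would allow it.

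**What to change.** In the SAP text below Table 2, and in Sensitivity analyses with Table 4, add one pre-specified sensitivity analysis of A1:

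- For each pairwise McNemar/Newcombe comparison, use the same FFA and the same valid follow-up period for both tests.
- Collapse both tests only over visits in that period at which both have a recorded result.
- For FFA-positive participants, require at least one such common visit in the 3 months before the FFA.

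Beside each test's sensitivity and specificity, report the median number of contributing visits per participant. State in advance that an A1 difference which disappears on common visits will be interpreted as possibly due to delivery. A1 stays the main analysis.

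The cost is SAP wording, a data step and some extra tables; no new data are needed. Each pair uses fewer visits, so a test's estimate can differ from pair to pair, and collapsed sensitivity can be lower than in A1 (65% against 80% for the fully delivered test in the 75% example). That is why this belongs beside A1 and not in its place.

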**Table 1 Timing of outcome collection**

Assessment	Recruitment	Routine visits (approx. every 8 weeks)	If any diagnostic test positive	If FFA positive	18 months	exit
Assessment of eligibility criteria	✓					
Written informed consent	✓					
Baseline vision and risk factors	✓					
Blood collection	✓			✓		✓
Diagnostic tests: 
 
• Subjective patient vision
 
• AMSLER
 
• Visual acuity
 
• OCT
 
• Fundus examination
 
• Autofluorescence (only if available)
 
	✓	✓			✓	✓
Reference standard: FFA	✓		✓		✓	✓
Post conversion case note review						✓
Upload of required imaging to reading centre for analysis	✓		✓		✓	✓

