### **Definition of valid follow-up period**

If a participant is included as defined above, then the valid follow-up period will be from baseline until the date of the last valid FFA (as defined above).

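### Analyses A4–A6 pair a reading-centre reference that does not end follow-up with index-test windows built for a local one, and have no rule for eyes the reading centre grades as nAMD at baseline

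*SAP*

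**What the plan says.** **Reference.** The SAP's list ahead of Table 3 makes reference standard B (reading-centre FFA, used in A4–A6) "positive if the reading centre FFA indicates nAMD at any time point" and negative only if there is no nAMD throughout.

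**Index windows.** A4–A6 reuse definitions A, B and C from A1–A3.
- A4: "All index tests during the valid follow-up period are used", and "the valid follow-up period will be from baseline until the date of the last valid FFA" (SAP, Definition of valid follow-up period). SAP Table 2 scores a true positive for any positive index result in that period.
- A5: "Only uses index tests within 6 months of" the participant's study end date.
- A6: definition C takes the result at the "last available visit only (within a 3 month window of the last FFA". The paragraph introducing the third index approach, labelled A3, says that if nAMD developed according to the reference standard, "only the index test data from their visit where nAMD was diagnosed will be used".

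**What ends follow-up.** Protocol 3.6.7 ends monitoring before 3 years on a clinical diagnosis of nAMD in the study eye or on withdrawal of consent. Nothing ends it on a reading-centre grade.

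**Baseline.** The row "Upload of required imaging to reading centre for analysis" in SAP Table 1 is ticked at recruitment, and Protocol 6.3 has the reading centre grade images from all the time points in the schedule independently. Eligibility rests on the routine-care FFA taken before consent (Protocol 3.6.4). The exclusion for nAMD found at baseline does not mention the reading centre.

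**The concern.** Under the local reference, the positive FFA normally leads to diagnosis and exit. The last FFA, the study end and the last visit then all fall close to conversion, and the three windows make sense. Under the reading-centre reference that link is broken for every eye on which the two readers differ. Such an eye can be monitored to 36 months, and none of the stated windows for A4 or A5 moves back to the FFA that made it diseased.

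Baseline disease is a second route to the same problem. An eye with a lesion that only the reading centre saw at entry can be counted among the converters. Visual acuity is positive on a fall of 10 or more letters from baseline, and Amsler on new or increased distortion. OCT and fundus evaluation are scored on the signs present. Mixing prevalent with incident disease can therefore affect the tests unequally, and A4–A6 make formal paired McNemar comparisons between them. These are the only analyses whose FFA reference is read independently of the site, so their definitions should hold up.

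**Working it through.** **Windows against a concrete case.** Take an eye graded positive by the reading centre at the 18-month FFA, negative locally, and followed to 36 months.

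| Analysis | Window as written | Consequence |
|---|---|---|
| A4 | Baseline to last valid FFA (36 months) | A first index positive at, say, 30 months makes a true positive, 12 months after the reading-centre finding |
| A5 | 30 to 36 months | An index positive at 18 months is ignored; if tests are negative from 30 months on, the eye is a false negative |
| A6 | Definition C: last visit, near 36 months. A3 wording: visit of diagnosis, 18 months | The two texts give different answers |

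The recency check does not close the gap. In the participant inclusion criteria, the 3-month rule applies only when the last FFA shows nAMD. An eye graded positive at 18 months and negative at exit enters under the looser rule for a negative last FFA, yet Table 2 and definition B count it as diseased. Nor do the criteria say whose reading is meant.

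**The plan's own figure, for scale.** The documents state no figure for A4–A6. The sample size for sensitivity uses a difference of 0.15, disagreement of 0.30, two-sided 5%, 90% power and 28% incidence:
- Cases = (1.960×√0.30 + 1.2816×√(0.30 − 0.15²))² / 0.15² = 135.9, so 136; 136/0.28 = 486, against 491 stated.
- 491/0.88 = 558, against 560 stated.
- Expected converters: 491 × 0.28 = 137.

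The sample size is not in dispute.

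**Late credit in A4 (assumed inputs).** Let g be the share of reading-centre-positive eyes followed on as locally negative (5–20%), s = 65% the sensitivity at the reading-centre-positive FFA, and q the chance per visit of a later positive (2–10%). Allow 9 further visits (18 months is about 78 weeks; 78/8 = 9.75). Only eyes missed so far can gain credit:
- Gain = g × (1 − s) × [1 − (1 − q)⁹]
- Low: 0.05 × 0.35 × 0.166 = 0.3 points
- High: 0.20 × 0.35 × 0.613 = 4.3 points

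**Prevalent eyes (assumed inputs).** Let f be the share of reading-centre-positive eyes already positive at baseline (5–20%). Change in sensitivity = f × (sensitivity in prevalent eyes − sensitivity in incident eyes).
- Change-based test, 65% in incident and 20–40% in prevalent eyes: 0.05 × (40 − 65) = −1.3 points to 0.20 × (20 − 65) = −9 points.
- Test scored on signs present, 80% in incident and 90–100% in prevalent eyes: 0.05 × (90 − 80) = +0.5 points to 0.20 × (100 − 80) = +4 points.
- Paired difference, planned at 15 points, with 90% against 20% in prevalent eyes: (1 − f) × 15 + f × 70 = 17.75, 20.5 and 26 points at f = 5, 10 and 20%. If both tests find 40% of prevalent eyes, it falls instead to 14.25, 13.5 and 12 points.

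**The case against.** **Baseline FFAs are arguably not outcome FFAs.** The SAP Method paragraph ties disease status to the follow-up period (naming the local FFA). The missing-data section distinguishes FFAs done after the baseline one, and inclusion in analysis A needs a follow-up FFA. This has force: it is not settled that a positive baseline grade alone makes an eye a case. But the valid follow-up period starts at baseline, definition B says any time point, and a lesion present at entry can be graded positive again later. No text removes that eye. How often this would happen is unknown.

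**A6 may already be anchored.** A reader of definition C alone might infer that A6 can look years past conversion. The documents do not support that firmly, because A3 and A6 share an index definition and the A3 text points to the diagnosis visit. What stands is a conflict to reconcile.

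**Late credit may be legitimate.** The planned measure is any positive during monitoring, so a later positive can be called delayed detection of real disease. That is a defensible target, but Protocol section 8 counts a true positive within a fixed period of the positive reference standard, and A5 as written departs from that anchor.

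**Change-based tests can still react.** One might infer that visual acuity and Amsler cannot detect a prevalent lesion. They can if it progresses. The supportable statement is that they may miss it more often. (Amsler is not collected at all after baseline distortion.)

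**Other protection exists.** Sensitivity analysis 1 substitutes reading-centre OCT for local OCT, so A4–A6 are not the only guard against a shared local reader, although the reference there is still the local FFA.

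**Conclusion.** The definitional gap is real for A4 and A5, the anchor for A6 is contradictory, and a rule for reading-centre positives at baseline is missing from all three. The analyses can be distorted; the documents do not show that they will be. Under the assumed ranges, prevalent eyes cost a change-based test about 1 to 9 points of sensitivity and late credit adds about 0.3 to 4 points in A4. For visual acuity and Amsler the two act in opposite directions, so the net sign is undetermined. If the readers agree, both are zero.

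Larger figures can be produced but should not be used. Adding 5 to 25 prevalent eyes to 137 converters and assuming none is ever detected gives 0.65 × 137/(137 + k) = 62.7% to 55.0%. With 20–40% detected, k = 25 gives 58.1–61.1%. Likewise, crediting 20–40% of all of 10 to 35 discordant eyes gives 1.4 to 8.1 points; restricting credit to the 35% missed gives about 0.5 to 2.8.

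A1 is largely unaffected, because a positive local FFA normally ends follow-up and eligibility was judged locally. The point concerns secondary analyses and is worth correcting before they are run.

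**What to change.** For A4–A6, amend the SAP to:
1. define reference standard B on post-baseline reading-centre FFAs;
2. exclude eyes the reading centre grades as nAMD on the baseline FFA, and report how many;
3. end the valid follow-up period at the first reading-centre-positive FFA;
4. count the A5 six-month window back from that FFA;
5. state that A6 uses the visit at that FFA, and reconcile definition C with the A3 paragraph;
6. say that the last FFA in the inclusion criteria means the reading-centre grade in these analyses.

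Eyes never graded positive keep the existing windows. Only the analysis changes: participant follow-up and data collection stay as they are. The cost is a few sentences and the loss of some participants from secondary analyses. The documents do not give the number; at the assumed 5–20% of about 137 reading-centre-positive eyes it would be 7 to 27 (137 × 0.05 = 6.9; 137 × 0.20 = 27.4).
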